Far Eastern Memorial Hospital

Human subject research study protocol

I. Title

Effects of individualized exercise intervention combined with manual therapy on the musculoskeletal system, cardiorespiratory endurance and quality of life in severe hemophilia patients with polyarthropathy.

II. Principal Investigator

[name] / Title: Physical Therapist

III. Co-Investigator

[name], [name] / Title: Physical Therapist

IV. Background

Hemophilia is clinically characterized by acute bleeding, more than 80% of which occur in specific joints (commonly occurring in ankle joints, knee joints and elbow joints, followed by hip joints, shoulder joints and wrist joints) and muscles (iliopsoas and gastrocnemius). Joint bleeding worsens joint damage in hemophilia patients, increasing the risk of chronic synovitis and hemophilic arthropathy in the long term. Improper treatment of intramuscular bleeding cause muscle contracture, especially in muscles that cross joints (such as calf muscles and psoas muscles), bleeding sites in these muscles are related to neurovascular damage and require immediate treatment to prevent permanent damage and loss of function [1].

For hemophilia patients with chronic synovitis who cannot take routine prophylaxis, the World Federation of Hemophilia recommends non-surgical treatment, including short-term prophylaxis for 6-8 weeks to control bleeding, selective COX-2 inhibitors, or physical therapy improves muscle strength and joint function to reduce pain and inflammation [6]. In addition, past studies have also recommended that patients with hemophilia receive physical therapy evaluation and intervention to improve muscle strength, balance, cardiorespiratory fitness, reduce the risk of falls, and improve quality of life [7].

A complete assessment of acute joint bleeding and physical therapy based on the clinical status of the case is necessary [3]. Past studies have shown that individualized exercise significantly improve muscle strength, upper and lower limb mobility [10], so individualized physical therapy should develop treatment plans and content based on the individual's abilities and goals [6].

Many literatures have discussed the safety and effectiveness of different physical therapy interventions for hemophilia patients and found that exercise therapy, manual therapy, electrotherapy and hydrotherapy, etc. improve muscle strength and

joint mobility [6][10][11]. Coupled with appropriate physical therapy, it can also strengthen muscles, increase joint stability, avoid joint contracture, and reduce the possibility of re-bleeding [2][4][7][8]. Past literature has recommended that exercise therapy should be provided to patients with hemophilia. However, there is currently no consensus on the type, severity, and frequency of safe exercise programs, especially for hemophilia patients with polyarthropathy [12][13]. In addition, manual therapy is another effective physical therapy intervention to increase biomechanical extensibility and joint function by mobilizing and stretching joints and soft tissues (including muscles and nerves). Although the use of manual therapy for patients with hemophilia is increasing, most studies focus on exploring the mobility of single joint [12][13], and the number of studies on manual therapy for multiple joints in the past literature is limited. As hemophilia patients' life expectancy increases, workforce participation, overall functioning, and independent activity daily living have become current issues and challenges. Therefore, much more evidence-based research is needed on manual therapy and exercise programs in hemophilia patients with polyarthropathy. Therefore, this study intends to investigate the impact and effectiveness of individualized physical therapy based on case conditions (severe hemophilia with polyarthropathy) [3]. It is hoped to try to combine different physical therapy techniques (manual therapy and exercise intervention) to improve pain, muscle strength, joint health, cardiopulmonary endurance, and thereby enhance the overall quality of life [5][7][8][9].

V. Purpose

Whether the use of individualized physical therapy combined with manual therapy and exercise intervention effectively improve joint status, muscle strength, pain, cardiopulmonary endurance, etc. for severe hemophilia patients with polyarthropathy, and at the same time prevent the possibility of recurrence of bleeding.

VI. Methods

A. Selection criteria and number of people.

1. Number of subjects: It is expected that 10 subjects.

2. Inclusion criteria:

- a. Over 20 years old and diagnosed with severe hemophilia
- b. Those who receive prophylaxis regularly
- c. There are more than 2 target joints (arthrosis)

3. Exclusion criteria:

- a. Unable to sign the informed consent form
- b. Any neurological disease or major musculoskeletal system disease (such

as fracture) one year ago

- c. Have had more than 3 (excluding 3) joint replacement surgeries (different joints)
- d. Unable to walk due to hemophilic arthropathy or any other disease
- e. Major bleeding events that pose risks or hinder research
- f. Unable to follow instructions due to cognitive impairment

4. Recruitment methods: through the Rehabilitation Department of Far Eastern Memorial Hospital, the Hemophilia Center and relevant hemophilia associations. Recruitment is open and a promotional leaflet has been given.
5. Method of consent of research subjects: After the assessment and confirmation of inclusion and before the start of the research, fully inform the experiment content and process, and ask the subjects to sign the human subject clinical trial consent form.

B. Design

1. Research conduct method
 - a. The physical therapists of the research team will evaluate whether they meet the inclusion criteria to recruit subjects who meet the conditions of this trial.
 - b. Fully inform the experiment content and process, and ask the subjects to sign the subject informed consent form.
 - c. Study location: Rehabilitation department
 - d. The execution content is as follows:
 - (i) Manual treatment: including fascia release, progressive passive stretching, joint mobilization, etc., and adjustments will be made according to the subject's current condition.
 - (ii) Exercise therapy: including upper and lower limbs muscle strengthening, trunk (spine) exercise, and adjustments based on the subject's current condition.

Upper extremity strengthening	
 • Shoulder external rotation (with theraband): 10 repetitions per set Position the upper arm and forearm at a 90-degree angle, holding the theraband with both hands. Rotate outward while keeping the upper arms close to the sides of the body throughout the movement. • Shoulder flexion (with theraband): 10 repetitions per set Hold the theraband in one hand, extend the arm upward to lift it straight, and then slowly lower it back down. • Shoulder abduction (with sandbag or theraband): 10 repetitions per set Hold a sandbag or theraband in one hand, and slowly lift
-------------------------------	--

	
the arm outward to the side until it is parallel to the floor.
 
 • Elbow flexion / extension (with theraband): 10 repetitions per set While seated, pull the theraband with one hand, performing elbow flexion and extension movements.
Lower extremity strengthening	
 • Hip & knee flexion/extension (with sandbag): 10 repetitions per set Stand with both hands supporting a stable table or chair. Attach a sandbag to one leg, perform hip and knee flexion, and then slowly extend the leg backward. • Hip abduction (with theraband): 10 repetitions per set Lie on your side with a theraband secured around both feet for resistance. Perform hip abduction by lifting the top leg outward against the resistance. • Ankle dorsiflexion/plantarflexion (with theraband): 10 repetitions per set While seated, attach a theraband to one ankle for resistance. Perform ankle dorsiflexion (lifting the foot upward) and plantarflexion (pointing the foot downward). • Ankle eversion/inversion (with theraband): 10 repetitions per set While seated, attach a theraband to one ankle for resistance. Perform ankle eversion (turning the foot outward) and inversion (turning the foot inward).
Trunk(spine) exercise	
 • Pelvic tilting: 10 repetitions per set Lie flat on your back with your knees bent and feet flat on the bed. Inhale as you tilt your pelvis forward, creating a hollow in the lower back; exhale as you tilt your pelvis

	
backward, pressing your lower back flat against the bed.
 
 • Thoracic spine rotation: 10 repetitions per set Lie on your side, and rotate the shoulder joint backward and outward as far as possible. This movement can be coordinated with breathing. • Abdominal core training: 10 repetitions per set While seated, lift your feet off the ground with both knees bent. • Dynamic neuromuscular stabilization: 10 repetitions per set Lie flat on your back with your hips and knees at a 90-degree angle. If it's difficult to maintain this position, use a ball or chair for support. Slowly inhale, allowing your abdomen to expand. Exhale slowly, trying to maintain the abdominal expansion without letting it collapse.
--	---

(iii) Exercise prescription settings:

- (1) Frequency: 10 times/time, 1~2 times/day, 3~5 days/week.
- (2) The time is 10 minutes, and the time can be gradually increased depending on the situation.
- (3) The intensity is adjusted in time according to the patient's condition: the sandbag can be gradually increased from 0.5 kg, and the elastic band can be gradually increased starting from the lightest resistance coefficient (from light to dark according to the color).

- e. Intervention schedule: Once a week for three months (about 12 weeks), 30 minutes of traditional physical therapy plus 30 minutes of individualized physical therapy intervention, about 1 hour.
- f. Questionnaires and scales were conducted before intervention, at the 6th week after intervention (mid-term intervention) and at the 12th week (end of intervention) to evaluate changes in joint status, pain, cardiopulmonary endurance, functional level, and quality of life.
- g. The patient daily note includes exercise duration and content, intensity, manual

therapy techniques, bleeding, and remark on special situations.

(i) Exercise duration and content, intensity, and manual therapy techniques:

Gradually increase according to the current situation and ability, as mentioned above.

(ii) Bleeding: It can be determined by the range of motion of the joint, the severity of the pain, and the appearance of redness, swelling and heat.

(iii) Notes on special circumstances: If there are any special things in this study, please note them down.

h. Subjects will be given NT\$500 each in the 6th and 12th weeks respectively, for a total of NT\$1,000 in traffic allowance.

2. Subject follow-up or necessary rehabilitation plan:

During the study period, subjects will come to the treatment room for individualized physical therapy once a week, and safety status will be tracked regularly.

After the study is completed, if necessary (depending on subject's opinion and therapist's judgment), rehabilitation plan will be arranged based on the actual situation.

3. Treatment effect evaluation and statistical analysis methods:

This study employed the non-parametric statistical software SPSS version 20.0, with a significance level set at $p < 0.05$. Descriptive statistics were used to describe the characteristics and distribution of the basic data variables. Furthermore, the Wilcoxon signed-rank test was utilized to examine differences in joint condition, muscle strength, pain, and cardiopulmonary endurance before intervention, and at 6 and 12 weeks post-intervention. The statistical analysis included comparisons between pre-test and mid-test, as well as pre-test and post-test, to mitigate the risk of incomplete data due to participants dropping out before completing the final test. Additionally, sample size calculations were performed using G*Power. The effect size was based on the visual analogue scale measuring perceived pain in patients with hemophilic knee joint disease, set at $d = -1.30$ [20]. With an alpha level of 0.05 and a power value of 0.95, the required sample size was determined to be 9 participants. To account for potential sample attrition, a 10% increase in sample size was applied, resulting in a projected total sample size of 10 hemophilia patients [12].

4. Questionnaires or other research-related scales:

This study utilized the following scales and questionnaires to assess changes in joint condition, pain, cardiopulmonary endurance, functional level, and quality of life in patients before intervention, and at 6 and 12 weeks post-intervention, in order to confirm treatment efficacy:

a. **Hemophilia Joint Health Score (HJHS):** This scale is designed to monitor joint

changes over time in hemophilia patients. It evaluates the swelling of the elbow, knee, and ankle joints, duration of persistent swelling, muscle atrophy, presence of crepitus during movement, reduction in range of motion, joint pain level, muscle strength, and overall gait performance. **Validity:** The scale has high evidence of both convergent validity and discriminant construct validity for detecting joint damage in adults with hemophilia, making it suitable for this population. **Reliability:** The scale demonstrates excellent reliability, with test-retest (ICC=0.89) and inter-observer (ICC=0.83) values.[14] The scale was assessed and completed by physical therapists.

- b. **Visual Analog Scale (VAS):** This scale evaluates pain in target joints of hemophilia patients, converting the results into scores to provide a clearer understanding of overall pain experience. **Reliability:** The scale exhibits high reliability with an ICC of 0.97 (95% CI 0.96 to 0.98). Research indicates that it is a reliable and valid instrument. [15]
- c. **6-Minute Walk Test (6MWT):** This test assesses the overall cardiopulmonary endurance of patients. **Reliability:** The reliability is good, with test-retest values ranging from 0.88 to 0.94. **Validity:** It has moderate convergent validity, with a correlation of 0.71 to 0.82 with treadmill performance. [16] The assessment and completion of this scale are performed by physical therapists.
- d. **Hemophilia Activity List (HAL):** This scale evaluates functional activities in hemophilia patients across seven domains: lower limb function, upper limb function, transportation, self-care, household tasks, leisure activities and exercise, and modification or use of assistive devices. **Validity:** The HAL demonstrates good construct and convergent validity. **Reliability:** It shows good internal consistency, with a Cronbach's alpha ranging from 0.61 to 0.96. [17] This scale is completed by the patients themselves.
- e. **EQ-5D-5L:** This scale assesses patients' quality of life, including mobility, self-care, usual activities, pain or discomfort, and anxiety or depression. **Validity:** It exhibits satisfactory construct validity for measuring quality of life in hemophilia patients. Research indicates that this scale has both good reliability and validity. [18] [19] The scale is completed by the patients themselves.
- f. **Patient Diary Card:** This card assesses patient status, including basic information and daily living activities, and records the content of each treatment session. The documentation is completed by physical therapists.

VII. Handling of Research Materials:

- A. Collection and processing of paper, electronic data / samples during the study:
The principal investigator is responsible for explaining the experimental procedures and distributing consent forms. The principal investigator also oversees the execution of exercise and manual therapy, while the co-investigator handles clinical

assessments and data statistics and analysis. All data is collected and processed by the research team. Paper records are securely locked in the principal investigator's personal filing cabinet, and electronic data is temporarily consolidated and stored on a personal computer.

B. Post-study processing, storage, and retention of paper and electronic data / samples:
To ensure the appropriate handling and security of the data, the research team will utilize a lockable filing cabinet to store paper records securely. Electronic data, once consolidated, will be saved on a personal computer. Upon completion of the study, all research data will be retained for five years. After this period, the principal investigator will be responsible for the destruction of electronic data to ensure privacy. Additionally, paper records containing personal information will be destroyed by incineration through a process managed by Far Eastern Memorial Hospital, to mitigate the risk of data leakage.

VIII. Protection of subjects' rights

A. Potential physical, psychological, and social harm and mitigation measures:
Although the likelihood is low, this study may still cause physical discomfort such as muscle soreness or joint bleeding due to the testing procedures. Therefore, prior to testing, participants will be asked if they regularly receive prophylaxis. If any discomfort occurs during the testing, the procedure will be immediately halted, and appropriate management will be taken. Should the discomfort occur three times, the subject will be withdrawn from the study ahead of schedule. During the testing period, professionals will assist in enhancing the safety of the subjects.

B. Conditions and mechanisms for study suspension / termination or early withdrawal:
Since rehabilitation outcomes may vary among individuals, the therapist will continuously monitor the subject's condition throughout the intervention period. Additionally, subjects may withdraw their consent to participate in the study at any time, and this decision will not affect the therapist's future medical care of the subject. Subjects need not worry about the impact of withdrawal on subsequent rehabilitation treatment (this will be explicitly stated in the consent form), thereby minimizing any psychological pressure or burden.

C. Subject compensation:
Subjects will receive transportation expenses of 500 TWD each at the 6th and 12th weeks, totaling 1000 TWD.

IX. Outcomes

A. Expected results and major benefits:

This study aims to investigate the therapeutic benefits of individualized physical therapy approach, combined with manual therapy and exercise interventions, for severe hemophilia patients with polyarthropathy. Based on previous research, manual therapy and exercise intervention have been shown to effectively improve musculoskeletal conditions. It is anticipated that this study will also enhance subjects' pain management, muscle strength, joint health, and cardiopulmonary endurance, ultimately improving overall quality of life.

B. Ownership and utilization of results:

Upon completion of the research, the results will be owned by Far Eastern Memorial Hospital.

X. Funding requirements and sources:

The funding for this study will be sourced from an internal project grant provided by Far Eastern Memorial Hospital.

XI. Conflicts of interest:

This trial is not sponsored by any manufacturers and does not have any commercial interests.

XII. References or domestic and international literature:

3. Johnny Mahlangu et al. WFH Guidelines for the Management of Hemophilia, 3rd edition. *Haemophilia*. 2020;26(Suppl 6), 88. DOI: 10.1111/hae.14046
5. Scaturro et al. (2022). Effectiveness of rehabilitation on pain and function in people affected by hemophilia. *Medicine*. 100:50, 1. doi: 10.1097/MD.oooooooooooo27863.
6. Adolfo Llinás et al. WFH Guidelines for the Management of Hemophilia, 3rd edition. *Haemophilia*. 2020;26(Suppl 6), 126. DOI: 10.1111/hae.14046

7. A. L. FORSYTH, D. V. QUON and B. A. KONKLE. Role of exercise and physical activity on haemophilic arthropathy, fall prevention and osteoporosis. *Haemophilia* (2011), 17, e870. DOI: [10.1111/j.1365-2516.2011.02514.x](https://doi.org/10.1111/j.1365-2516.2011.02514.x)

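### No bleed-free window is set before baseline, so recovery from a non-major joint bleed could be read as treatment efficacy; net bias arises only if bleeds are commoner at entry than at follow-up

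*Combined protocol and SAP*

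**What the plan says.** - **Entry rules.** Exclusion e (VI.A.3) is the only criterion about bleeding: "Major bleeding events that pose risks or hinder research". *Major* is not defined and no period is given. The one look-back in the criteria, a year in exclusion b, concerns neurological and major musculoskeletal disease. Inclusion b requires prophylaxis ("Those who receive prophylaxis regularly") and inclusion c requires more than two target joints. Neither asks for a stable or bleed-free period.
- **Check before testing.** VIII.A says that "prior to testing, participants will be asked if they regularly receive prophylaxis". It mentions no question about recent bleeds.
- **How a bleed is recognised.** VI.B.1.g(ii): "It can be determined by the range of motion of the joint, the severity of the pain, and the appearance of redness, swelling and heat". Bleeds go into the daily note, but no rule uses that record to time a measurement or adjust an analysis.
- **What the outcomes score.** On HJHS, VI.B.4.a says "It evaluates the swelling of the elbow, knee, and ankle joints, duration of persistent swelling". It goes on to list loss of motion, joint pain, strength and gait, among other items. VAS (VI.B.4.b) scores pain in the target joints.
- **Analysis.** There is one measurement before intervention, then weeks 6 and 12 (VI.B.1.f). VI.B.3 compares pre with mid and pre with post by the Wilcoxon signed-rank test. There is no control arm, and VI.B.4 treats the change as confirming efficacy.

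**The concern.** Three of the plan's own bleed signs (joint motion, pain and swelling) are also HJHS items, and pain in a target joint is the VAS. A subject measured at baseline during a resolving target-joint bleed would score worse than usual on the outcomes themselves. If the bleed settles by week 6 or 12, the score improves whether or not the treatment works. With about 10 subjects, a few large improvements can take the top ranks of a signed-rank test. Nothing in the design would show that this had happened, and if the date of the last bleed is not recorded at baseline it may be impossible to reconstruct later.

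**Working it through.** **1. The plan's sample size.** Inputs from VI.B.3: |d| = 1.30, alpha 0.05 (sidedness not stated), power 0.95. Using noncentral-t power with the effective size n × 3/π for the signed-rank test, one-sided power is 0.940 at n = 8 and 0.964 at n = 9. So n = 9, as stated. Then 9 × 1.10 = 9.9, rounded up to 10. The steps below use n = 10.

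**2. Ceiling on false improvement, with bleeds at baseline only.** Assume no treatment effect and no ties, and let k subjects with resolving bleeds show the k largest improvements. The ranks sum to 55. At two-sided 0.05, improvement is significant when the improved ranks sum to at least 47, that is, when the worsened ranks sum to at most 8. The worsened ranks are then a random subset of {1, …, 10 − k}, so

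P = (number of subsets of {1, …, 10 − k} with sum ≤ 8) / 2^(10 − k).

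Sets of distinct positive integers summing to 0, 1, …, 8 number 1, 1, 1, 2, 2, 3, 4, 5, 6, in total 25. At k = 3 the set {8} is no longer available, which leaves 24. At one-sided 0.05 the limit is 10 instead of 8, and the counts are 43, 42, 40 and 37.

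| k | two-sided 0.05, favourable tail | one-sided 0.05 |
|---|---|---|
| 0 | 25/1024 = 2.4% | 43/1024 = 4.2% |
| 1 | 25/512 = 4.9% | 42/512 = 8.2% |
| 2 | 25/256 = 9.8% | 40/256 = 15.6% |
| 3 | 24/128 = 18.8% | 37/128 = 28.9% |

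These are per outcome and per visit. The documents do not give k; 1 to 3 is an assumed range. At k = 1 the total two-sided error does not change: it was 2 × 25/1024 = 4.9% and is still 25/512 = 4.9%. What changes is that all of it now falls on the favourable side.

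**3. Softer recovery.** Suppose recovery is an assumed 1 to 3 SD of the change score, without guaranteed top ranks. Simulation (200,000 runs per case) then gives favourable rejection of 3.9–4.9% (k = 1), 6.1–9.6% (k = 2) and 9.5–18.1% (k = 3). The shift in mean change is k × recovery / 10, or 0.1–0.3 SD per affected subject.

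**4. How many subjects might be affected.** The documents give neither a bleed rate nor a recovery time. Assume b = 1 to 4 bleeds per subject-year and a window of w = 2 to 6 weeks, with p = 1 − exp(−b × w/52). This gives p = 0.038 to 0.370, or 0.4 to 3.7 of 10 subjects. A constant rate gives the same expected number at weeks 6 and 12 as at baseline.

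**5. Bleeds at follow-up as well.** Simulated at n = 10 with no treatment effect and an assumed 1–3 SD shift per bleed:

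| chance of bleed at baseline | at follow-up | false improvement | false worsening |
|---|---|---|---|
| 10–30% | the same | 2.4–2.5% | about 2.4% |
| 30% | 10% | about 7–12% | below 1% |
| 0 | 10–30% | 0.1–1.3% | 4–24% |

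False benefit therefore needs more bleeding at entry than at follow-up. The last row shows that a bleed-free baseline with nothing done at later visits tilts the comparison the other way.

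**The case against.** A reader might infer that the gap by itself makes a false positive likely. The strongest reply is that the ceiling in step 2 places bleeds only at baseline. Nothing keeps weeks 6 and 12 free of bleeds, and with equal chances at every visit the effects cancel. That reply stands, and it limits the conclusion.

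A reader might also infer an excess of bleeds at entry from recruitment through the Rehabilitation Department and the Hemophilia Center. That is plausible, but no section says that candidates come because of a recent bleed. VI.A.4 also recruits openly by leaflet and through hemophilia associations, and regular prophylaxis is required.

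Exclusion e already lets the team turn away major bleeds that would hinder the research, so the gap concerns non-major or resolving ones. A muscle bleed away from the scored joints need not move HJHS or VAS. The documents state no size of recovery, so a large fall in scores cannot be taken as given.

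Finally, replacing exclusion e with a timing rule would remove the only criterion that excludes bleeding events posing a risk. A deferred candidate can still enrol later, so a timing rule does not do that job.

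None of this supplies a rule that times baseline relative to a non-major bleed, or a way to recognise an affected comparison.

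**Conclusion.** The gap holds, with its consequence stated as a possibility. A baseline could be taken during a non-major, resolving joint bleed, and the plan could not separate recovery from efficacy. The documents do not show that this will happen, or how often.

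If 1, 2 or 3 of 10 subjects are affected and none bleeds at follow-up, the favourable-tail error rises from 2.4% to at most 4.9%, 9.8% or 18.8%. With an assumed 30% of subjects affected at baseline and 10% at follow-up, it is about 7–12%. With equal frequency at all visits there is no net bias; the bleeds add noise and cost power. These figures rest on the assumed numbers of entries and sizes of recovery above. The plan should be changed because the change is cheap, but the point does not invalidate the trial. The wider limitation, an uncontrolled comparison with a single baseline, would remain after the fix.

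**What to change.** 1. Keep exclusion e unchanged. Beside it, add a measurement-timing rule: if a joint or muscle bleed, judged by the signs in VI.B.1.g(ii), occurred within a fixed window before baseline, the baseline HJHS, VAS and 6MWT are deferred and the candidate is re-screened. The Hemophilia Center sets the window length, and the protocol states it.
2. Record the date and site of the last bleed in the same way at baseline, week 6 and week 12.
3. In VI.B.3, prespecify a sensitivity analysis of the pre-mid and pre-post comparisons that leaves out any pair with a bleed inside the window at either visit. The full analysis stays the main one: deferral at baseline alone can tilt it toward worsening, and the sensitivity analysis treats both visits alike.
4. Report bleeds during follow-up as outcomes, since preventing recurrent bleeding is part of the stated purpose (V). Leaving out affected pairs must not hide them.

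The cost is a few later starts, one extra question per visit and one extra analysis. That analysis may be small: with five pairs the smallest two-sided p-value is 2/2^5 = 0.0625, so with that few pairs it can only be descriptive.

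### With one group and only before-after tests, the plan can estimate change during a combined programme but cannot confirm efficacy of that programme or of its individualized part

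*Combined protocol and SAP*

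**What the plan says.** **Treatment.** VI.B.1.e sets one weekly schedule for all subjects over about 12 weeks: "30 minutes of traditional physical therapy plus 30 minutes of individualized physical therapy intervention, about 1 hour". Traditional physical therapy is not defined, and the protocol does not say whether subjects were already receiving it before enrolment.

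**Group structure.** VI.A.1 expects 10 subjects in total. No section mentions arms, allocation, a control, a run-in or a repeated baseline. The term single-arm is not used; it is inferred from these facts, and nothing contradicts it.

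**Analysis.** VI.B.3 plans Wilcoxon signed-rank tests, baseline against week 6 and baseline against week 12, for pain, joint condition, muscle strength and cardiopulmonary endurance, at p < 0.05.

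**Aim.** V asks "Whether the use of individualized physical therapy combined with manual therapy and exercise intervention effectively improve joint status" and other outcomes, and whether the therapy can "at the same time prevent the possibility of recurrence of bleeding". IX.A gives as its aim the therapeutic benefit of the individualized approach. VI.B.4 says the scales assess changes, and the same sentence ends by saying that this is done to confirm efficacy. VI.B.1.f describes the same assessments more modestly, as serving "to evaluate changes in joint status, pain, cardiopulmonary endurance, functional level, and quality of life". No section limits the interpretation.

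**The concern.** A signed-rank test on change scores asks whether the typical change is zero. The aim asks whether treatment caused the change and, in V and IX.A, whether the individualized approach did. These are different questions, and the plan does not say so.

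A significant result could therefore be read as meeting the stated aim, even if the improvement came from the traditional half-hour, from familiarity with the walk test, from expectation, or from the passage of time. The bleeding question is worse placed, because no planned comparison addresses it at all.

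**Working it through.** **1. The plan's sample size belongs to a one-group comparison.** Inputs from VI.B.3: |d| = 1.30, alpha 0.05, power 0.95, result 9, raised to 10. Sidedness is not stated. For a paired comparison, power is P(T > t) with T noncentral t, noncentrality d√m and m − 1 degrees of freedom. Here m = n for the t test, and m = 3n/π for the signed-rank test with normal changes.

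- One-sided signed-rank, n = 9: m = 27/π = 8.594; noncentrality 1.30 × √8.594 = 3.811; power 0.964. At n = 8 power is 0.940. So n = 9.
- One-sided t: n = 8 (power 0.950).
- Two-sided t: n = 10 (0.954).
- Two-sided signed-rank: n = 11 (0.964).
- Attrition: 9 × 1.10 = 9.9 and 9/0.90 = 10, so 10 either way.

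The stated 9 is reproduced as a within-subject calculation. The plan is sized to detect change, not a difference from a comparator.

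**2. What the change contains.** Write a subject's change from baseline as

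D = T + I + N + error,

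where T is the effect of traditional therapy, I that of the individualized manual therapy and exercise, and N everything else (time, repeat testing, expectation). Every subject receives T and I together and is exposed to N. The data inform only the sum T + I + N.

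- The test's null is T + I + N = 0.
- Efficacy of the programme is a statement about T + I. It needs N, which nothing in the design estimates.
- Efficacy of the individualized part is a statement about I. It needs T as well.
- A larger sample estimates the sum more precisely but does not split it.

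Expectation is a live component: HAL and EQ-5D-5L are self-completed, therapists complete HJHS and the walk test, and no blinding is described.

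**3. Bleeding.** The daily note in VI.B.1.g records bleeding during the study. No pre-intervention bleeding measure is described, and bleeding is not among the outcomes tested in VI.B.3. There is neither a before-after contrast nor a between-group one.

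**4. The outcome lists also differ.**

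| Outcome | V | VI.B.1.f | VI.B.3 tests | VI.B.4 |
|---|---|---|---|---|
| Joint status or condition | yes | yes | yes | yes |
| Pain | yes | yes | yes | yes |
| Cardiopulmonary endurance | yes | yes | yes | yes |
| Muscle strength | yes | no | yes | no |
| Functional level | no | yes | no | yes |
| Quality of life | no | yes | no | yes |
| Bleeding | yes | no | no | no |

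A restated objective must follow the VI.B.3 column, or VI.B.3 must be extended.

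**5. Illustration of size.** Assume T + I = 0, normal change scores, n = 10 and a two-sided exact test. Of the 2^10 = 1,024 sign patterns, 25 give a rank sum of 8 or less, so each tail has 25/1,024 = 0.0244 and the test's true size is 0.0488. By simulation, the chance of significance in the favourable direction is:

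| Assumed N (SD of change) | Chance of p < 0.05, favourable |
|---|---|
| 0 | 2.4% |
| 0.2 | 7.9% |
| 0.5 | 28% |
| 1.0 | 78% |

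The shifts are assumptions; the protocol gives no size for non-specific change.

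**The case against.** **Small before-after studies are acceptable, and V and IX.A only pose a question or a forecast.** Much of this stands. The design is a fair choice for 10 subjects, V is phrased as a question, and the forecast in IX.A is not an inference. The outright overclaim is the closing clause of VI.B.4. V and the aim sentence of IX.A still need the limit, because they set the question that the tests will be taken to answer.

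**If subjects were already on stable traditional therapy, the change would say more about the added part.** This is correct: T would then be largely in the baseline. But the protocol neither requires nor records it, and N would remain.

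**The rejection rates are only a power curve.** They are. They show how the test responds to any shift, whatever its cause. A reader might take them as the chance of a false efficacy claim in this trial; the documents give no figure that would support that.

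**Stronger readings that the documents do not support.**

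- A reader might infer that VI.B.1.f alone is worded to match the tests. It is not: VI.B.4 also speaks of assessing changes, and the VI.B.1.f list of outcomes differs from that in VI.B.3.
- A reader might infer that regression to the mean is built in. Eligibility sets no threshold on pain, HJHS or walking distance, so it is possible but not designed in.
- A reader might infer that the weekly visit contradicts the exercise prescription of "10 times/time, 1~2 times/day, 3~5 days/week". The two can coexist as visits and exercise between visits. The text could be clearer, but that is a separate matter and this point does not rest on it.
- A reader might infer that the title must change. It names effects in general terms and can stand if the aim carries the limit.

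**Conclusion.** The concern holds as a mismatch between claim and design. The planned tests can show change over 6 and 12 weeks during a combined programme. They cannot confirm efficacy of the programme, cannot isolate its individualized part, and cannot address prevention of bleeding. This follows from the structure of the plan and does not depend on the illustrative rates or on the sample-size arithmetic, which is consistent with a one-group comparison.

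It rests on one inference, that all subjects follow the single described schedule with no comparator. A reader might go further and conclude that the trial is invalid or needs a control arm. The documents do not compel that: the study is workable as an estimate of change, provided it says so. The wording should be corrected before results are reported, since it determines what the trial may conclude.

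**What to change.** 1. **VI.B.4.** Keep the wording about assessing changes. Replace the closing clause about confirming efficacy with: *to estimate change from baseline during the combined programme*.
2. **V, and the aim sentence of IX.A.** State the objective as: *to estimate the 6-week and 12-week change in pain, joint condition, muscle strength and cardiopulmonary endurance during a combined programme of traditional physical therapy plus individualized manual therapy and exercise*. Name functional level and quality of life here only if VI.B.3 adds HAL and EQ-5D-5L to the same signed-rank comparisons.
3. **V, bleeding.** State that bleeding is recorded descriptively over the study period and that no preventive effect can be concluded.
4. **VI.B.3.** Add: *Because there is no comparator, change cannot be attributed causally to the programme, or separately to its individualized part.*

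The cost is a few sentences in four sections. Design, test type and sample size are unchanged. The downside is a more modest conclusion.
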